Exploring the role of tryptophan metabolites in pediatric migraine

2023.05.01

1. Research objectives, study content and key questions to be addressed

1.1 Research objectives This research focuses on the key scientific issues of "tryptophan metabolites and childhood migraine", and explores the pathogenesis, diagnosis, treatment, and prevention of childhood migraine by combining clinical characteristics and medical history and other multi-level data, with the aim of establishing an assessment system for early identification and intervention of childhood migraine, systematically developing an individualized treatment and assessment system for childhood migraine, and conducting clinical translational research in the field of childhood migraine. We aim to establish an assessment system for early identification and intervention of childhood migraine, systematically carry out individualized treatment and assessment system for childhood migraine, and conduct clinical translational research in the field of childhood migraine. The following are the details: The aim of the study is to establish a system for the early identification and intervention of migraine in children, and to systematically develop an individualized treatment and evaluation system for migraine in children.

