2.1 Experimental protocol

2.1.1 Inclusion and exclusion criteria of study subjects

Case group inclusion criteria:(1) Age 4-18 years old, male and female are not limited. (2) Meet the diagnostic criteria of ICHD-3 with aura, without aura, and chronic migraine. (3) Migraine was diagnosed by two or more specialized neurologists. (4) PedMIDAS score > 11 (5) Migraine had never been treated (6) Patients and families gave informed consent to the study purpose, significance, risks, benefits, and informed consent. Source: Department of Pediatrics Outpatient and Inpatient Unit, Oilu Hospital. Shandong University

Inclusion criteria for the control group:(1) Age 6-18 years, male and female. (2) Did not meet the diagnostic criteria of ICHD-3 migraine and other headaches. (3) Physical health allowed their participation in the study. (4) Patients and their families gave informed consent to the study purpose, significance, risks, benefits, and information of the study. Source: Department of Pediatrics Outpatient and Inpatient Unit, Oilu Hospital. Shandong University.

Exclusion criteria:

(1) presence of drug overdose (2) autoimmune diseases (3) neurological diseases other than migraine, intracranial masses (4) congenital or hereditary diseases (5) diabetes, bronchial asthma, cardiovascular diseases, pulmonary diseases (6) other types of primary and secondary headache.

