2.1.2 Data collection

(1) Data sources: questionnaires, outpatient medical records and auxiliary examination results.

(2) Collection methods: questionnaire survey, medical records review, blood collection.

(3) Data composition: Basic personal information, migraine triggering factors, clinical features of headache, medication, past medical history, ancillary examinations, and blood samples were collected from all enrolled headache patients.

① Basic personal information included name, gender, age, height, weight (calculated BMI) cultural level, residence address, and contact information.

② Migraine triggering factors: genetic factors, endocrine (menstruation), diet (cheese, chocolate, puffed food), psychological factors (sleep, anxiety, depression, emotional stress, etc).

③ Clinical characteristics of headache included: whether the patient was in the attack phase or inter-attack phase, the location of the patient's headache, the nature of the headache, the degree of pain (assessed using the visual analog scale VAS Appendix), the duration of the disease (years), the frequency of the headache, the duration of each headache, the time of the last pain, the presence of aura, aura symptoms, concomitant symptoms (photophobia, phonophobia, nausea, vomiting, gastrointestinal

symptoms),exacerbation and remission. The information of each headache, duration of last pain,presence of aura, aura symptoms, concomitant symptoms (photophobia, photophobia.nausca, vomiting, gastrointestinal symptoms), aggravation and relief factors, familyhistory, etc.

④Also record medication use, past medical history, ancillary test results such asroutine blood, liver function, kidney function, lipids, blood glucose, ECG, TCD, headCT,head MRIhead MRA examination,etc.PedMIDAS scale score, migraine treatment efficacy assessment scale, headachediary

⑤5ml of venous blood

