2.1.4 Data analysis

Statistical analysis was performed using SPSS26.0 software analysis, and statisticaldata were tested for normality, and the mean standard deviation ($x + S$) was used formeasurement data that conformed to the normal distribution, and one-way ANOVAwas applied for comparison between the three groups, and t-test for two independentsamples was used for comparison between two groups. The correlation between theplasma levels between migraine attacks and the duration of the disease was analyzedby SPSS26.0 correlation analysis.

(1) After completing the questionnaire survey, the researchers collected data

and analyzed the risk of migraine in children due to the interaction of multiple factors, and used logistic regression to screen the indicators related to the risk of migraine in children due to the interaction of multiple factors, and established an early assessment model of migraine in children to achieve early detection, early diagnosis and early prevention of migraine in children.

(2) Based on the collected medical history, different group analyses were performed, and the plasma levels of tryptophan metabolites in migraine patients were compared with those in healthy controls by t-test; one-way ANOVA was performed on the plasma levels of tryptophan metabolites between different types of migraine; correlation analyses were performed between the frequency, duration, severity and two types of migraine attacks; and logistic regression was performed to screen for possible influences on the risk of migraine in children. Logistic regression was performed to screen the factors that may influence the diagnosis of migraine in children.

(3) To analyze the diagnostic value of tryptophan metabolite and tryptophan metabolite combined diagnosis by ROC curve, and to analyze whether there is any statistical difference between the three diagnostic indexes by independent sample t-test, and to evaluate the diagnostic indexes of tryptophan metabolite and tryptophan metabolite combined diagnosis by diagnostic test, and to evaluate the diagnostic indexes of tryptophan metabolite and tryptophan metabolite combined diagnosis as the possibility and accuracy of specific diagnostic indexes for migraine in children were evaluated.

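### The logistic model in SAP 2.1.4(1) is claimed to serve early detection and prevention, but its data can show only association with, and discrimination of, already diagnosed migraine

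*SAP*

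**What the plan says.** **Purpose.** SAP 2.1.4(1) describes an analysis that "used logistic regression to screen the indicators related to the risk of migraine in children due to the interaction of multiple factors" and that thereby "established an early assessment model of migraine in children to achieve early detection, early diagnosis and early prevention of migraine in children". Section 1.1 gives the same aim for the project as a whole: to "establish an assessment system for early identification and intervention of childhood migraine".

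**Cases.** Section 2.1.1 requires that children "Meet the diagnostic criteria of ICHD-3 with aura, without aura, and chronic migraine". It adds "Migraine was diagnosed by two or more specialized neurologists", "PedMIDAS score > 11" and "Migraine had never been treated". No criterion limits the time since onset.

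**Controls.** Under 2.1.1 these are children who meet criteria neither for migraine nor for another headache. Section 2.1.3 recruits them as a separate group of healthy children.

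**Duration.** Section 2.1.2 records disease duration in years. The opening paragraph of 2.1.4 correlates plasma levels with it. The logistic model in 2.1.4(1) makes no use of it.

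**The concern.** A model for early detection or prevention has to rest on information available before the disease is established. Here every case is diagnosed before entry, and the candidate predictors are recorded at or after that point. A variable that changed because of migraine enters the regression in the same way as one that came before it, and the fit cannot tell the two apart. Sampling by case status adds a second limit: the model's intercept carries the proportion of cases that the investigators chose to recruit.

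What is at stake is the claim attached to the result. A model presented as a tool for early detection and prevention invites use in children outside the study. What it will have been shown to do is separate children with recognised migraine from children without headache.

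**Working it through.** The SAP gives no case:control ratio, population frequency or model performance, so it has no figure to reproduce. The check has two parts.

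**1. Claim against design**

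| What the claim needs | What the SAP provides |
|---|---|
| Predictors measured before onset, or children followed to onset | Recruitment of diagnosed cases and healthy controls; no observation before onset and no follow-up to onset described (2.1.1, 2.1.3) |
| Cases early in their disease | Never-treated cases with PedMIDAS above 11 and no upper limit on duration (2.1.1) |
| Comparison with children in whom the diagnosis is still open | Controls without headache; other headache types are an exclusion criterion (2.1.1) |

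The candidate predictors in 2.1.2 fall into two kinds.

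- *Can change after onset:* sleep, anxiety, depression, emotional stress and BMI; also metabolite level, if it is entered. An odds ratio for any of these may reflect cause, consequence or both.
- *Fixed before onset:* genetic factors and family history. Migraine in the child cannot alter these, so reverse causation does not apply to them.

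**2. Predicted probabilities, if any were issued**

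With sampling by case status, where π is the frequency of migraine in the target population:

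logit(fitted) = logit(true) + ln[(cases/controls) × (1 − π)/π]

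On the odds scale:

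true odds = fitted odds × (controls/cases) × π/(1 − π)

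Assumptions, none of them in the SAP: 1:1 recruitment and π of 5% or 10%.

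- Intercept shift: ln(0.95/0.05) = 2.94 at 5%; ln(0.90/0.10) = 2.20 at 10%.
- Fitted 80% has odds 0.8/0.2 = 4.
  - π = 5%: 4 × 0.05/0.95 = 0.2105, and 0.2105/1.2105 = 17.4%.
  - π = 10%: 4 × 0.10/0.90 = 0.4444, and 0.4444/1.4444 = 30.8%.
- Fitted 50% has odds 1, and becomes 5% and 10%.

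Sensitivity of the fitted 80% to the assumptions:

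| Cases:controls | π = 2% | 5% | 10% | 15% |
|---|---|---|---|---|
| 1:1 | 7.5% | 17.4% | 30.8% | 41.4% |
| 2:1 | 3.9% | 9.5% | 18.2% | 26.1% |

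The shift affects only the intercept. The odds ratios are unchanged by it.

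**The case against.** **No predicted risks are planned.** The regression is described as a screen for indicators. That rests on odds ratios, which remain estimable under case-control sampling. The SAP nowhere says that probabilities or risk scores will be issued. This stands, and it makes the intercept point conditional.

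**The size depends on the setting.** The ratio and the frequency are both assumed. In a clinic that sees many children with migraine, as 2.1.5 describes, the frequency could exceed 10% and the distortion would shrink. This stands too; the figures are an illustration.

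**The SAP does look at duration and restricts treatment history.** It plans a correlation of plasma levels with disease duration, and it admits only never-treated cases, which plausibly moves the case mix towards first presentation. Both are relevant. But the correlation does not enter the logistic model, and a child can be untreated for years, so neither makes the cases early.

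**Early diagnosis can mean earlier recognition of existing migraine.** Discrimination among diagnosed cases is a legitimate first step towards that, and part of the wording reads as a long-term aim. This is fair as to the aim. Section 2.1.4(1), however, presents early detection and prevention as what the fitted model will deliver.

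**Conclusion.** The plan attributes to the model a property that its design lacks. Fitted to diagnosed cases of unlimited duration and separately recruited controls, the model can support statements about association with diagnosed migraine and about discrimination from controls. It cannot support a claim of early detection or prevention. This part rests on the SAP's own text and on no numerical assumption.

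The second part is conditional. If predicted probabilities were issued without correction, a fitted 80% would correspond to 17–31%, given an assumed 1:1 ratio and an assumed frequency of 5–10%.

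A reader might infer more, and the document does not support it:

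- *That the model has no value for early recognition or risk.* This is too absolute. The odds ratios survive the sampling, and fixed factors such as family history are not open to reverse causation.
- *That the study will publish inflated risks.* The SAP does not say that it will publish any.
- *That the cases have long-standing disease.* The distribution of duration is unknown. The criteria leave it open, and the never-treated requirement may shorten it.
- *That limiting the fit to recent-onset cases would rescue the claim.* Those children are still diagnosed, still selected by the PedMIDAS threshold and still measured after onset.

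**What to change.** In SAP 1.1 and 2.1.4(1):

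1. State that the logistic model distinguishes diagnosed migraine from controls, and remove the early-detection and early-prevention claims.
2. Report odds ratios and discrimination only.
3. Issue no predicted risks unless the intercept is reset to a stated external frequency, with its source. Even then the result refers to existing migraine and not to future onset.
4. Optionally, add a sensitivity analysis that refits the model with cases of short recorded duration, using one cut-off fixed in advance. It can show whether the associations depend on duration; it should not carry an early claim.

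Items 1 to 3 are changes of wording and reporting and need no new recruitment. The downside is a narrower conclusion. Item 4 uses the duration already recorded, but its estimates will be less precise, and with no sample size in the SAP it cannot be said whether the subset would support a multivariable fit.

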1.2 Research content

1.2.1 Exploration of the pathogenesis of migraine in children For the subjects included in the study, blood was collected at any time during the first 2-4 hours of the headache attack in migraine patients; blood was collected at least 24 hours before and after the inter-episode period without headache attack in migraine patients. In healthy controls, blood was collected in a quiet state. Tryptophan metabolite levels were measured by ELISA. The plasma levels of tryptophan metabolites were analyzed in different groups according to the collected medical histories, and the plasma levels of migraine patients were compared with those of healthy controls by t-test: one-way ANOVA was performed between different types of migraine: correlation analysis was performed between the frequency, duration, severity and two types of migraine attacks; logistic regression was performed to screen for possible factors. The results of the above analyses were combined to explore the pathogenesis of migraine in children and to lay the foundation for the improvement of the diagnosis of migraine in children and the development of new drugs.

1.2.2 Exploration of specific diagnostic indexes for migraine in children For the subjects included in the study, blood was collected at any time during the first 2-4 hours of the headache attack in migraine patients, and blood was collected at least 24 hours before and after the headache attack in the inter-episode period in migraine patients. Tryptophan metabolite levels were measured by ELISA. The ROC curve was used to analyze the diagnostic value of the combined diagnosis of tryptophan metabolites, and tryptophan metabolites, and the area under the curve (AUC) of tryptophan metabolites and the combined diagnostic indexes of both were subjected to independent sample t-test to analyze whether there was a statistical difference between the three, and the diagnostic test evaluation indexes were used to evaluate the combined diagnosis of tryptophan metabolites, and tryptophan metabolites respectively, and to evaluate them as The possibility and accuracy of the

specific diagnostic index of migraine in children were evaluated.

2. The proposed research method, technical route, experimental protocol and feasibility analysis.

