2.1.3 Study method

(1) The trial was reviewed by the Research Ethics Committee of Qilu Hospital of Shandong University. Patients were obtained from the pediatricoutpatient clinic of Qilu Hospital of Shandong University, with written permissionfrom parents or guardians and, where appropriate, consent from the children. Theinvestigators were responsible for design, data collection, analysis, and interpretation. Data were collected by field researchers. and all data were confidential for theduration of the trial; trialists and data analysts could not communicate data with eachother. Eligible healthy children and children with migraine were recruited in the first step and basic information about the children and headache characteristics were obtainedby the site staff, and blood was retained from the study subjects for Elisa assay, respectively.

(2) Method for determination of tryptophan metabolite content:

①Timing of blood collection

In the case group, blood was collected at any time during the first 2-4 hours of themigraine attack; in the inter-migraine attack group, blood was collected at least 24hours before and after the headache-free period. In the healthy control group, bloodwas collected in a quiet state.

②Storage and testing methods

5 ml of elbow venous blood was collected from patients and healthy children inpurple tubes, and the samples were immediately transferred to ice-cold glass tubescontaining a mixture of anticoagulant and protease inhibitor, and centrifuged at 3000rpm for 5 minutes at 4°C. The supernatant was stored at -80°C, and tryptophanmetabolite levels were measured by ELISA, and the case and control groups were compared and analyzed.

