2.1.5 Feasibility analysis

(1) The Elisa kit technology and medical statistics technology used in this project have been widely and maturely applied in other biomedical research fields, and this project has all the core technology reserves that can guarantee the successful completion of the subject.

(2) The PICU of Qilu Hospital of Shandong University, which has rich experience in scientific research and clinical medicine, as well as rich clinical cases, is sufficient to meet the needs of scientific research; we have sufficient strength in terms of scientific research strength, talent demand and economic support to ensure the successful completion of our experiment.

(3) The pediatric outpatient clinic of Qilu Hospital of Shandong University receives a large number of children with migraine every day, and the severity of the disease is complex and diverse, so the number and diversity of children with migraine are sufficient to meet the needs of our experiment.

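### Diagnostic accuracy of the metabolite indexes is estimated in the only cohort described, with no pre-set cut-off or internal validation, and the screened early assessment model has no planned performance check.

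*SAP*

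**What the plan says.** Section 2.1.4 contains two analyses that bear on this point.

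- **Item (1), the model.** The investigators "used logistic regression to screen the indicators related to the risk of migraine in children due to the interaction of multiple factors" and from the result "established an early assessment model of migraine in children to achieve early detection, early diagnosis and early prevention of migraine in children". Item (2) adds a further screen: "Logistic regression was performed to screen the factors that may influence the diagnosis of migraine in children". No candidate list, entry rule, significance level or shrinkage is given. No AUC, sensitivity, specificity or calibration is attached to the model.
- **Item (3), the metabolite indexes.** The stated purpose is "To analyze the diagnostic value of tryptophan metabolite and tryptophan metabolite combined diagnosis by ROC curve". Section 1.2.2 adds that "the diagnostic test evaluation indexes were used to evaluate the combined diagnosis of tryptophan metabolites". Both places speak of three indexes, which reads as two markers and their combination. How the markers are combined and how a cut-off is chosen are not stated.

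The data source is described once, in 2.1.3: "Eligible healthy children and children with migraine were recruited in the first step". The SAP mentions no split, cross-validation, bootstrap, pre-set threshold or second cohort.

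**The concern.** When a threshold or a set of weights is chosen on the same children in whom accuracy is then measured, the choice follows chance features of that sample. The resulting figures are apparent performance, which on average exceeds what the same rule achieves in other children. Item (3) is meant to support a conclusion about how accurate the metabolites are as a specific diagnostic index, so this bias falls on the study's main diagnostic claim.

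Item (1) has a different gap. A model intended for early detection and prevention is built by data-driven screening, and nothing in the plan would show whether it works.

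This is separate from the choice of test for comparing AUCs. Replacing the independent-sample t-test in item (3) with a paired AUC comparison would not remove in-sample optimism.

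**Working it through.** The SAP gives no sample size, effect size, AUC, sensitivity or specificity, so there is no figure to reproduce. The size of the bias can only be shown under assumptions.

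**Inputs from the SAP:** two markers plus a combination (1.2.2 and 2.1.4 item (3)); one cohort of cases and healthy controls (2.1.3).

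**Assumed:** equal groups of 30 to 200; independent normal markers, each shifted by 0.5 SD in cases; logistic combination; cut-off maximising sensitivity + specificity − 1 (Youden).

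**Step 1: best achievable accuracy under these assumptions.**
- Combined separation: δ = √(0.5² + 0.5²) = 0.707.
- AUC = Φ(δ/√2) = Φ(0.50) = 0.691.
- Sensitivity = specificity = Φ(δ/2) = Φ(0.354) = 0.638 at the best cut-off.

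**Step 2: apparent performance against 6000 new children** (simulation, 400 runs per row).

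| Per group | AUC apparent / new | Excess | Sens/spec apparent | Sens/spec new |
|---|---|---|---|---|
| 30 | 0.708 / 0.676 | 0.032 | 0.724/0.671 | 0.633/0.600 |
| 50 | 0.705 / 0.683 | 0.022 | 0.700/0.669 | 0.638/0.610 |
| 100 | 0.695 / 0.687 | 0.008 | 0.671/0.661 | 0.632/0.623 |
| 200 | 0.693 / 0.689 | 0.004 | 0.658/0.652 | 0.635/0.628 |

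A separate simulation at 40 per group gave sensitivity/specificity of about 0.69/0.69 apparent and 0.61/0.63 in new children. The Youden index is then 0.69 + 0.69 − 1 = 0.38 against 0.61 + 0.63 − 1 = 0.24. In every row the mean apparent values lie above the ceiling in Step 1.

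**Step 3: where the bias comes from.** A single marker with a 0.5 SD effect at 50 per group shows no AUC excess (0.636 apparent, 0.636 new). Its sensitivity/specificity are still 0.661/0.614 apparent against 0.606/0.569 new. The data-chosen cut-off therefore does most of the harm, with or without a combination.

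With no signal at all, mean apparent AUCs at 40, 60 and 100 per group were:
- combined index: 0.578, 0.567, 0.551;
- one single marker: 0.552, 0.542, 0.533;
- better of the two markers: 0.572, 0.561, 0.547.

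The combination's built-in advantage is 0.026, 0.025 and 0.018 over one marker, and 0.006, 0.006 and 0.004 over the better one.

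**Step 4: the item (1) model, for illustration only.** Suppose it were scored in the children used to build it. With 16 pure-noise candidates (9 triggers and 5 personal items counted from 2.1.2, plus 2 metabolites) screened at an assumed p<0.10, the mean apparent AUC was about 0.64, 0.62 and 0.60 at 40, 60 and 100 per group, against a true 0.50. With 20 candidates, 3 of them real at 0.5 SD, it was 0.769 apparent against 0.671 in new children at 50 per group, and 0.743 against 0.715 at 200.

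**The case against.** A reader might infer that the early assessment model will be reported with inflated AUC, sensitivity and specificity. The SAP does not support that. ROC and diagnostic-test evaluation are planned only for the metabolites and their combination, and a figure that is not planned cannot be too high. For that model the defect is the missing assessment.

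The candidate count in Step 4 is also uncertain. Section 2.1.2 says that "migraine triggering factors, clinical features of headache, medication, past medical history, ancillary examinations, and blood samples were collected from all enrolled headache patients", and 2.1.3 mentions only basic information and headache characteristics. Nothing shows that triggers were recorded in controls, so 9 of the 16 candidates may be unusable for separating cases from controls.

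A reader might also infer that over-fitting will make the combined index beat the single markers. Under no signal, its edge over the better marker is under 0.01, which is too small to carry that claim.

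Other points stand as limits. The SAP does not say that the combination is a fitted score. Use of the same children is inferred from there being only one cohort. Optimism is a statement about averages, not about every realised sample. With 100 or more per group and a real effect, the AUC excess is under 0.01.

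None of this supplies a cut-off rule or a validation step. The threshold bias persists for a single marker and for a combination formed by some other rule.

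**Conclusion.** The point holds in two parts.

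1. **Item (3) and 1.2.2:** followed as written, the plan yields apparent accuracy that is too high on average. The excess is modest for the AUC of a two-marker index, about 0.01 to 0.03 at 30 to 100 per group. It is larger for sensitivity and specificity if the cut-off is chosen on the same data, about 0.08 and 0.06 at 40 per group (0.69 − 0.61 and 0.69 − 0.63).
2. **Item (1):** a screened model is built with no plan to assess or validate it. Scoring it later in the same children could mislead badly, but the Step 4 figures only illustrate that risk.

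The direction of the bias follows from the design. Its size rests on assumed group size, effect size, logistic weighting, Youden cut-off and screening level, none of which the SAP gives.

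**What to change.** Amend 2.1.4 items (1) and (3), and 1.2.2 to match:

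- Limit candidate predictors to variables recorded in both cases and controls, and list them in advance.
- State how the markers are combined, and fix the cut-off rule before the data are analysed.
- Repeat the whole procedure (screening, fitting and cut-off choice) within each bootstrap resample or each fold of a repeated cross-validation.
- Report optimism-corrected AUC, sensitivity and specificity beside the apparent values, and add the calibration slope for the early assessment model.
- Base the accuracy conclusion and the comparison of combined with single markers on the corrected values.
- State that external validation is still needed before any diagnostic use.

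No extra children or assays are required. The cost is SAP wording, some scripting, and reported accuracy that will look slightly less favourable.

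### The case-control comparison of metabolite levels is an unadjusted t-test, so a sex, age or body-size imbalance between the groups can be mistaken for a migraine difference

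*SAP*

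**What the plan says.** - **Case-control comparison.** SAP 2.1.4(2): "the plasma levels of tryptophan metabolites in migraine patients were compared with those in healthy controls by t-test". The opening of 2.1.4 makes the two-group test one for independent samples. No covariate is named.
- **Other group comparisons.** The opening of 2.1.4 compares three groups, not named there, by one-way ANOVA. For migraine types, 2.1.4(2) says "one-way ANOVA was performed on the plasma levels of tryptophan metabolites between different types of migraine". Again no covariate is named.
- **Eligibility.** SAP 2.1.1 admits cases at "Age 4-18 years old, male and female are not limited", and controls of either sex at 6 to 18 years. It describes no matching or frequency balancing.
- **What is recorded.** SAP 2.1.2(3), item 1: "Basic personal information included name, gender, age, height, weight (calculated BMI) cultural level".
- **In whom.** The lead-in to that list says the items and "blood samples were collected from all enrolled headache patients". SAP 2.1.3(1) is wider: "Eligible healthy children and children with migraine were recruited in the first step and basic information about the children". It does not itemise what the basic information contains.
- **Multivariable analysis.** Logistic regression is the only one. It is used in 2.1.4(1) to screen risk indicators and build an early assessment model, and in 2.1.4(2) to screen possible factors. Its variables are not listed.
- **Diagnostic use.** SAP 1.2.2 and 2.1.4(3) take the metabolites into a ROC analysis as a possible specific diagnostic index.

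**The concern.** In a case-control comparison the raw difference in means contains the migraine difference plus whatever follows from differences in make-up between the two groups. Randomisation does not remove the second part, and this document describes no design step that would. If the share of girls, the age mix or body size differs between the groups, and the metabolites vary with them, a t-test cannot separate the two parts.

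The eligibility criteria already allow the age mix to differ, because cases may be 4 or 5 years old and controls may not.

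The consequence reaches past the t-test. The same levels go into the ROC curve, so separation that comes from sex or body size would count as diagnostic accuracy. A fixed bias is also not cured by recruiting more children: the standard error shrinks around the wrong value, and the false-positive rate rises.

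**Working it through.** **No stated figure to reproduce.** The SAP gives no sample size, alpha, standard deviation or effect size. What follows illustrates sex alone, and every input is an assumption.

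**Inputs (assumed).** Metabolite difference between girls and boys d = 0.2, 0.3, 0.5 within-sex SD. Case-control gap in the share of girls g = 0.1, 0.2, 0.3, with 50% girls among controls. n = 40, 60, 100 per group. Two-sided alpha 0.05. No true migraine effect.

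**Step 1, bias of the raw difference.** Bias = d × g.
- Smallest: 0.2 × 0.1 = 0.02 SD.
- Largest: 0.5 × 0.3 = 0.15 SD.

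**Step 2, false-positive rate.** Control variance v0 = 1 + 0.25d². Case variance v1 = 1 + d²(0.5 + g)(0.5 − g). SE = √[(v0 + v1)/n]. Rate = Φ(bias/SE − 1.96) + Φ(−bias/SE − 1.96).
- Largest case: v0 = 1.0625, v1 = 1.04, SE = √(2.1025/100) = 0.145, bias/SE = 1.034, rate = 0.179.

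| d | g | bias (SD) | n = 40 | n = 60 | n = 100 |
|---|---|---|---|---|---|
| 0.2 | 0.1 | 0.02 | 0.051 | 0.051 | 0.052 |
| 0.3 | 0.2 | 0.06 | 0.058 | 0.062 | 0.070 |
| 0.5 | 0.2 | 0.10 | 0.072 | 0.083 | 0.106 |
| 0.5 | 0.3 | 0.15 | 0.100 | 0.126 | 0.179 |

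The full range is 5.1% to 17.9%. With d of 0.2 to 0.3 and g of 0.1 to 0.2 it stays at about 5% to 7%.

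**Step 3, carry-over into the ROC.** With normal levels within each sex and no migraine effect, AUC = 0.5 + g[Φ(d/√2) − 0.5].
- Smallest: 0.5 + 0.1(0.556 − 0.5) = 0.506.
- Largest: 0.5 + 0.3(0.638 − 0.5) = 0.541.

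**Step 4, precision after adjusting for sex.** With overall share of girls p = 0.5 + g/2, R² of group on sex = (g²/4)/[p(1 − p)], and VIF = 1/(1 − R²). The variance ratio adjusted/raw is 2 × VIF/(v0 + v1).
- d = 0.5, g = 0.1: VIF 1.010, ratio 0.95.
- d = 0.2, g = 0.3: VIF 1.110, ratio 1.10.

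Adjustment removes the bias if the model is right, but it can gain or lose a little precision.

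**Step 5, does another analysis already adjust?** The logistic regression has migraine status as outcome and selects factors. Nothing in 2.1.4 puts sex, age or body size beside the metabolite, and nothing ties that model to the t-test or the ROC. A screen may also drop a confounder.

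**The case against.** **No imbalance is shown.** The document reports no difference in sex or body size and no effect of either on the metabolites. This stands: the raw difference can be confounded, and nothing here shows that it is.

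**Matching may sit in the protocol.** The independent-samples test argues against pair matching but does not exclude frequency balancing. This stands as a limit: the most that can be said is that this document describes none.

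**Covariates in controls.** A reader might infer that height and weight are available for every child. SAP 2.1.2 ties the list to headache patients, and 2.1.3 extends only un-itemised basic information to healthy children. Recording in controls is therefore not established.

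**The logistic regression might include sex and BMI.** It might, and its variables are open. For the same reason it cannot be counted as a planned adjustment.

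**Stronger sizes.** A reader might add a body-size bias, say 0.4 SD × correlation 0.3 = 0.12 SD, to a sex bias of 0.10 SD. The resulting 0.22 SD gives rejection rates of 22% at 60 and 34% at 100 per group (noncentral t). That needs both biases to point the same way. If they oppose, the net 0.02 SD gives 5.1% to 5.2%. The document supports neither direction.

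**Free precision.** A reader might also claim a gain, such as 1/0.85 = 1.18 (18% more children) if covariates explain 15% of variance. The document gives no such share, and the figure presumes balanced groups, whereas the bias argument presumes imbalance.

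**Migraine types.** That ANOVA contains cases only, so absence of matching to controls is no argument against it.

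**Conclusion.** The concern holds for the case-control comparison. The SAP fixes an unadjusted test for a non-randomised contrast, describes no design protection on sex or body size, lists the obvious covariates, and plans no adjusted comparison of levels. An imbalance can then be mistaken for a migraine difference.

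The size is unknown from the document. For sex alone, under the assumed ranges, it runs from negligible to material: error rates near the nominal 5% for modest effects and gaps, up to about 18% at the unfavourable end, with a null AUC of up to about 0.54. The case for change rests on confounding control and low cost. It does not rest on a demonstrated imbalance, on a gain in precision, or on any matching argument about the comparison between migraine types.

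**What to change.** 1. In 2.1.4(2), make the main case-control comparison a linear model of metabolite level (log-transformed if skewed) on group, with age and sex as covariates. Report the adjusted difference with a 95% CI, and keep the raw t-test as descriptive.
2. Reconcile 2.1.2 with 2.1.3 and state whether height and weight are recorded in controls. If they are, add BMI-for-age z-score to the model and name the growth reference. Raw BMI changes with growth and is not comparable across this age span.
3. Force the same covariates into the logistic model that contains the metabolites, so that the screen cannot drop them.
4. The comparison between migraine types can use the same covariates.

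Cost: SAP wording and a few more lines of analysis, a few degrees of freedom, and possibly a slight loss of precision if the groups are imbalanced (variance up to about 10% higher in the sex-only illustration). Children without height or weight drop out of the model with the z-score unless imputed, so the SAP should say how they are handled.
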